2.0 PROTOCOL SUMMARY

2.1 Study Synopsis

Name of Sponsor(s): Galecto Biotech AB	Compound: GB0139 (previously known as TD139)	
Title of Protocol: GALACTIC-1 - A randomized, double-blind, multicentre, parallel, placebo-controlled phase 2b study in subjects with idiopathic pulmonary fibrosis (IPF) investigating the efficacy and safety of GB0139, an inhaled galectin-3 inhibitor administered via a dry powder inhaler over 52 weeks	IND No.: 124075	EudraCT No.: 2018-002664-73
Study Number: GALACTIC-1	Phase: IIb	
Co-ordinating Investigator	 Keck School of Medicine of USC University of Southern California Department of Medicine Division of Pulmonary, Critical Care and Sleep Medicine [name]	
Overview (Figure 1) Population: All subjects enrolled into the study will have a diagnosis of IPF established within the previous five years, and a diagnostic HRCT scan assessed according the ATS/ERS/Fleischner criteria available within the previous 12 months (up to 12 months +27 days). Treatment: All subjects eligible for the study will be randomised in a 2:1 ratio to one of two treatment arms: A. GB0139 3mg once a day (2x 1.5mg capsules) by inhalation B. Placebo once a day (2x placebo capsules) by inhalation The stratification at randomization and the following SoCs are removed in Protocol version 6.1_UK such that all future participants will not be treated with nintedanib or pirfenidone at screening and ranodmisation: The two strata of Standard of Care (SoC) were as follows in the previous study design: 
 1. SoC1: Subjects currently on treatment with either pirfenidone or nintedanib. 2. SoC2: Subjects not currently treated with pirfenidone or nintedanib. 		

Evaluation and follow up: From baseline to week 52, visits will be scheduled at weeks 0, 4, 8, 12, 26, 40 and 52 for evaluations according to the Time & Events Table (Section 2.2). A subject's follow-up safety assessment will be performed via a phone call one week after the last study visit.	
Number of Subjects Estimated to randomize approximately 141 participants in total	
Dose Level(s) 
• GB0139 3mg once a day (2x 1.5mg capsules) by inhalation• Placebo once a day (2x placebo capsules) by inhalation	
Duration of Treatment & Follow up 
• 52-weeks treatment after randomisation• Follow up via a phone call one week after the last study visit	
Main Criteria for Inclusion 
1. Male and female subjects aged ≥ 40 years of age with a diagnosis of IPF established during the previous five years according to ATS/ERS/Fleischner criteria. A historical diagnostic HRCT scan assessed according to the ATS/ERS/Fleischner criteria must be available from within the 12 months (up to 12 months +27 days) prior to screening. Diagnostic HRCTs will be subject to central reading for confirmation.2. Lung function parameters as follows:
a. FVC $> 45\%$ of the predicted value at screeningb. DLCO (corrected for Hb) of 30% to 79% of the predicted value at screening.3. Patients who currently are not being treated with nintedanib or pirfenidone; or cannot tolerate nintedanib or pirfenidone.4. Subjects must sign and date a written, IRB/EC approved informed consent form and any required authorization prior to initiation of any study procedures.	
Main Criteria for Exclusion Subjects meeting any of the following exclusion criteria are not to be enrolled in the study/randomized to treatment: 
1. Currently has significant airways obstruction: FEV1/FVC ratio of < 0.7 at screening.2. Has clinical evidence of active infection, including, but not limited to, bronchitis, pneumonia, sinusitis, urinary tract infection, and cellulitis.3. Has a history of malignancy within the last 2 years with the exception of basal cell carcinoma, squamous cell carcinoma of the skin (localised, treated or cured), chronic lymphocytic leukaemia (under observation) and prostate cancer requiring anti-androgens, localised treatment (minor surgery, radiotherapy) and/or managed by observation.4. Has any condition other than IPF that, in the opinion of the investigator, is likely to result in the death of the subject within the next 2 years.	

5. Presence of other disease that may interfere with testing procedures or in the judgement of the Investigator may interfere with trial participation or may put the patient at risk when participating in this trial.
6. Is likely to receive lung transplantation within the next 12 months.
7. Currently receiving nintedanib, pirfenidone, high dose corticosteroid, cytotoxic (e.g., chlorambucil, azathioprine, cyclophosphamide, methotrexate), vasodilator therapy for pulmonary hypertension (e.g., bosentan). Also see prohibited medications (Section 8.3.2). A current dose of less than or equal to 15 mg/day of prednisone or its equivalent is acceptable if the dose is anticipated to remain stable during the study.
8. Prior use of GB0139 or previously randomised in GALACTIC-1.
9. Prior use of nintedanib or pirfenidone within 7 days of initiation of screening.
10. Prior use of investigational drugs within 30 days (or 5 half-lives, whichever is longer) of initiation of screening.
11. Participating in another interventional clinical trial.
12. Has a history of unstable or deteriorating cardiac or pulmonary disease (other than IPF) within the previous six months, including, but not limited to, the following:
 - a. Unstable angina pectoris or myocardial infarction, or percutaneous coronary intervention within the last 6 months
 - b. Congestive heart failure requiring hospitalization
 - c. Uncontrolled clinically significant arrhythmias.
13. If female, the subject is pregnant or lactating or intending to become pregnant before participating in this study during the study and within 33 days after last dose of the study drug; or intending to donate ova during such time period.
14. Woman considered to be of childbearing potential who do not use highly effective birth control methods during the study and for 33 days after last administration of study drug.
15. Male partners of women of child bearing potential not committing to using condoms during the course of the study and 90 days after last administration of study drug, unless they have undergone male sterilization.
16. Hypersensitivity to the active substance (GB0139) or the excipient (lactose).

Study Objectives

Primary Objectives

- Evaluate the effect of GB0139 dry powder for inhalation compared with placebo over 52 weeks treatment period on the annual rate of decline in FVC in participants with IPF who are not treated with or cannot tolerate nintedanib or pirfenidone.

Secondary Objectives

- Further characterize the effect of GB0139 compared with placebo over 52 weeks treatment period on FVC, also on the quality of life, time to respiratory-related hospitalizations and all-cause mortality.

Main Criteria for Evaluation and Analyses

Primary Endpoint

- The annual rate of decline in Forced Vital Capacity (FVC; expressed in mL over 52 weeks)

Key Secondary Endpoints

- Proportion of subjects with an absolute decline from baseline in FVC % pred of $\leq 10\%$ at w52.
- Change from baseline in St. George's Respiratory Questionnaire (SGRQ) total score at w52.
- Time to first hospitalization (respiratory related, including acute exacerbation of IPF).
- Time to death (all-causes).

Additional secondary and exploratory efficacy variables with bearing on the efficacy of GB0139 (e.g., other QoL) are described in detail in the Main Criteria and Evaluation and Analyses below).

Other Secondary Endpoints

- Proportion of subjects with an absolute decline from baseline in FVC % pred of $\leq 5\%$ at w52
- Change from baseline in 6-minute walk test (6MWT) distance over 52 weeks
- Change in diffusion capacity of the lung for carbon monoxide (DLCO), corrected for Hb
- Change from baseline at week 52 for dyspnoea assessment by University of California San Diego - Shortness of Breath Questionnaire (UCSD - SOBQ)
- Change from baseline at week 52 for HRQoL as assessed by Short Form Survey (SF-36)
- Percentage of subjects with Adverse Events (AE) or Serious Adverse Events (SAE)
- Time to first hospitalization (IPF related, including acute exacerbation of IPF)
- Time to first hospitalization (all cause)
- Time to respiratory related death
- Time to initiation of nintedanib or pirfenidone
- Change in FVC expressed in mL over 52 weeks for subjects who have never been treated with pirfenidone or nintedanib

Exploratory Endpoints

- **Biomarkers:** Change from baseline of selected biomarkers. These may include but are not limited to: YKL-40, PAI-1, PDGF-BB, MCP-1, CCL-18, Gal-3, markers of collagen metabolism.
- Time to initiation of pirfenidone or nintedanib treatment for SoC2 participants up to the time when SoC1 and SoC2 were removed in the study
- **Pharmacogenetics:** The study includes a pharmacogenetic component. This is not mandatory in order for a subject to participate in the study.

Statistical Considerations:

The primary efficacy analysis will be based on the comparison between the GB0139 3mg group against the Placebo group in patients who were not treated with nintedanib or pirfenidone at screening.

The primary endpoint of this trial, annual rate of decline in FVC, will be analyzed by a random coefficient regression model including treatment group and baseline FVC (mL).

The key secondary endpoints will be analysed as follows: Proportion of participants with an absolute decline from baseline in FVC % predicted of $\leq 10\%$ at week 52 will be analysed by logistic regression including treatment and baseline FVC (mL) in the model.

Change from baseline in the SGRQ total score at week 52 will be analysed by a mixed model repeated measure.

The time to first hospitalization (any respiratory related) will be analysed by a Cox PH model.

Time to death (all-causes) will be analysed by Cox PH model.

Secondary and further endpoints will be analysed in an exploratory manner.

Sample size justification:

The annual decline in FVC for placebo is estimated to be 200ml. To detect a difference from placebo in the decline of FVC of 100ml with a standard deviation of 240ml at the significance level of 10%, a sample size of 141, with a randomization ratio of 2:1, the study would have 75% power.

2.2 Study Time and Events Schedule

Table 1: Study Time & Events Schedule

Visit	1	2	3	4	5	6	7	8	Withdrawal ⁹	Follow up ⁷
	Screening ¹	Baseline	Treatment							
Weeks of treatment		0	4	8	12	26	40	52	-	
Day Time window	6 weeks	0	29 ±3	57 ±3	85 ±3	183 ±7	281 ±7	365 ±7		7 days after final study visit (+7 days)
Informed consent	X									
HRCT sent to central review	X									
Demographics (including height, weight)	X									
Medical history	X									
Randomization		X								
In- /exclusion criteria	X	X								
Physical examination, vital signs	X	X	X	X	X	X	X	X	X	
HRQoL (SGRQ, SF-36)		X			X	X		X		
Dyspnoea index (UCSD-SOBQ)		X			X	X		X		
12-lead ECG	X	X	X	X	X	X		X	X	
Laboratory test (chemistry, haematology) ²	X	X	X	X	X	X	X	X	X	
Urinalysis	X		X	X	X	X	X	X	X	
Pregnancy test ^{3, 4}	X	X	X	X	X	X	X	X	X	
Biomarker sample		X	X		X	X		X		
Genetics sample ⁵		X								
Spirometry (FVC, FEV1)	X	X	X	X	X	X	X	X	X	
SpO ₂		X						X		
DLCO	X							X	X	
6MWT		X						X	X	
Administer 1st study medication (at clinic) & inhaler training ⁶		X								
Dispense trial drug		X	X	X	X	X	X			
Compliance / drug accountability ⁷			X	X	X	X	X	X	X	
Adverse events & conc. meds ⁸	X	X	X	X	X	X	X	X	X	X

Notes:

1. HRCT confirmation by central reading must be obtained as soon as possible following screening visit 1 and prior to visit 2
2. See [Table 2](#) and [Table 3](#) Section 10.4.9

3. In women of childbearing potential only: serum b-HCG will be required at visit 1 only, followed by urinary testing at subsequent visits.
4. This is optional and separate consent must be obtained. The sample can be taken at other study visits.
5. Subjects should be observed for 1 hour after the first dose to monitor for any acute adverse effects of study drug administration (e.g., bronchospasm – see Section 8.1)
6. Includes checking the subject's use of the DPI device (Plastiape monodose inhaler)
7. The follow-up will be performed via a phone call.
8. Events occurring prior to randomization and administration of drug are considered as pre-treatment (as defined in Section 11.1.1). Adverse events are also collected for up to the phone follow up.
9. FVC, DLCO and 6MWT will be performed as part of the withdrawal assessments.

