10.4.7 Health-related Quality of Life Questionnaires

Three patient-reported assessments related to symptoms and quality of life will be collected during the study. A version of each will be to the site and will be completed by each subject at the visits as per the T&E table Section [2.2](#)

- St George's Respiratory Questionnaire (SGRQ) a validated QoL for IPF
- The Short Form Health-36 survey
- The University of California San Diego, shortness of breath questionnaire (UCSD-SOBQ)

10.4.8 12-Lead Electrocardiogram

Safety monitoring by ECG will be performed using site local equipment. PR interval, QRS duration, QT interval and QTcF are required to be evaluated.

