10.6 Withdrawal of Subjects from the Study

Subjects may withdraw for the following reasons:

- Lost to follow-up
- Study terminated by sponsor
- Withdrawal by subject
- Completed study
- Death
- Lung transplant
- Other (cause to be elaborated on in the subject's file)

All study procedures outlined for the withdrawal visit will be completed as specified in the Time and Events Table (Section 2.2). The primary reason for study drug discontinuation will be recorded on the eCRF.

Following the study withdrawal, no new information will be collected from the withdrawn subject and added to the existing data or any database.

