## 5.2 Definition of Analysis Visits

Assessments will be mapped to analysis visits for a variable as follows:

- Find the closest non-missing, within time-window (as per Table 1 below) result taken to the scheduled day as per the protocol schedule of assessments.
- If two assessments are equal distance either side of the scheduled day, then take the earlier result.

	Plus-Project Statistical Analysis Plan	
	Protocol Number: GALACTIC-1	Version: 1

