#### 7.2.3.2 Change from baseline in St. George's Respiratory Questionnaire total score at Week 52.

Data from an external central vendor (Clario/ERT) with the SGRQ results will be used. The details of scoring are provided in Section 11.6.

A Mixed Model with Repeated Measures (MMRM) will be fitted to the change from baseline in the SGRQ Total Score across all visits (Weeks 12, 26 and 52 - see Section 11.2). Treatment, visit, baseline SGRQ Total Score, and treatment-by-visit interaction will be fitted as fixed effects. A restricted maximum likelihood (REML) approach will be used, and an unstructured covariance structure shared across treatment groups will be used to model the within-subject errors. If the model fails to converge, a heterogeneous Toeplitz structure (TYPE=TOEPH option in PROC MIXED rather than TYPE=UN) will be used. The Kenward-Roger's correction to degrees of freedom will be applied.

Domain scores will be summarized by treatment group and visit only.

	Plus-Project Statistical Analysis Plan	
	Protocol Number: GALACTIC-1	Version: 1

The analysis will be repeated by subgroup (separately for each subgroup factor of interest). A fixed effect for the subgroup factor will be added and all interaction terms between treatment, visit and the subgroup factor will be included. The comparisons between treatments at each visit will be assessed within each level of the subgroup.

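### The withdrawal visit omits SGRQ, SF-36 and UCSD-SOBQ, so study leavers give no closing score for the key secondary SGRQ endpoint, and those with no Week 12, 26 or 52 score drop out of its model

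*Protocol*

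**What the plan says.** Protocol Table 1 has two questionnaire rows, beginning "HRQoL (SGRQ, SF-36" and "Dyspnoea index (UCSD-SOBQ". Both are marked at baseline and Weeks 12, 26 and 52 and are blank under Withdrawal. Spirometry, DLCO and 6MWT are marked there, and note 9 confirms it: "FVC, DLCO and 6MWT will be performed as part of the withdrawal assessments". The SAP schedule (11.2) has the same blanks and the same note.

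The rest of the protocol defers to that table. Section 10.4.7 says the questionnaires "will be completed by each subject at the visits as per the T&E table Section" 2.2. Section 10.6 says "All study procedures outlined for the withdrawal visit will be completed as specified in the Time and Events Table", and then closes the door: "Following the study withdrawal, no new information will be collected from the withdrawn subject and added to the existing data or any database". Participants who only stop treatment may stay in the study and attend the remaining scheduled visits (Protocol 6.2 and 10.5).

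SAP 7.2.3.2 fits an MMRM to change from baseline in the "SGRQ Total Score across all visits (Weeks 12, 26 and 52", with baseline SGRQ as a covariate. SAP 7.2.4.4 and 7.2.4.5 use the same model for UCSD-SOBQ and SF-36. Off-schedule results are assigned to visits by the rule in SAP 5.2: "Find the closest non-missing, within time-window (as per Table 1 below) result taken to the scheduled day".

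**The concern.** SGRQ is a key secondary endpoint; 6MWT and DLCO are ordinary secondary endpoints. At a withdrawal visit that takes place anyway, the lower-ranked measures get a closing value and SGRQ does not. Because nothing is collected after withdrawal, that visit is the last opportunity.

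Two groups are affected:

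- **Leavers with no post-baseline SGRQ.** They have no response record in the MMRM. They belong to the mITT set that SAP 4.3 names for the key secondary endpoints, but add nothing to the SGRQ estimate.
- **Leavers with a Week 12 or Week 26 score.** They contribute that score, and the model predicts the rest under missing at random. The gap between scheduled scores is 14 weeks (Week 12 to 26) and then 26 weeks (Week 26 to 52), so the last score may be up to 26 weeks old.

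The SAP offers no remedy for SGRQ. Missing data are generally not imputed (7.1.2), and the missing-data sensitivity analysis concerns FVC only (7.2.2.4 and 11.3). For another key secondary endpoint, the FVC % predicted responder, subjects lost to follow-up are counted as having declined by more than 10% (7.2.3.1). SGRQ has no such provision.

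**Working it through.** **1. The plan's own figure.** The documents state no power, SD or dropout rate for SGRQ. The only design figure is for FVC: 141 subjects at 2:1 (94 and 47), difference 100 mL, SD 240 mL, two-sided 10%, 75% power. SE = 240 × √(1/47 + 1/94) = 42.9; 100/42.9 = 2.33; 2.33 − 1.645 = 0.69; power = Φ(0.69) ≈ 75%. This reproduces. The present point does not depend on it; only the 141 is used below.

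**2. Precision lost through leavers with no post-baseline SGRQ.** Assume a fraction d of the 141 leave the study before any such score, evenly across arms, and that precision is proportional to the number contributing. Number lost = 141 × d; SE multiplier = 1/√(1 − d).

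| d (assumed) | Lost from the MMRM | SE multiplier |
|---|---|---|
| 2% | 2.8 (about 3) | 1.01 |
| 5% | 7.1 (about 7) | 1.03 |
| 10% | 14.1 (about 14) | 1.05 |
| 15% | 21.2 (about 21) | 1.08 |

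The loss is small over a plausible range of 2–5%, and modest even at 15%.

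**3. When bias arises.** Let p be the share of an arm lacking a Week 52 SGRQ through study withdrawal, and δ the amount by which their true mean change differs from what the model predicts from their observed data. The arm mean is off by roughly p × δ, and the treatment difference by p₃δ₃ − p₀δ₀ (3 mg and placebo). If δ is zero in both arms (missing at random holds), the bias is zero however unequal p is. If δ is not zero, each SGRQ point of δ at p = 5% moves that arm's mean by 0.05 × 1 = 0.05 points. The documents give no basis for a value of δ.

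**4. Would marking the Withdrawal column be enough?** Take the SAP 5.2 windows, assume scheduled SGRQs fall on Days 85, 183 and 365, and let withdrawal occur on any day from 2 to 364 (363 days).

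| Withdrawal day | Window | Fate of the withdrawal SGRQ | Days |
|---|---|---|---|
| 2–71 | Weeks 4, 8 | Not a model visit | 70 |
| 72–84 | Week 12 | Enters | 13 |
| 85 | Week 12 | Coincides with the scheduled visit | 1 |
| 86–134 | Week 12 | Loses to Day 85 (closest-day rule) | 49 |
| 135–182 | Week 26 | Enters | 48 |
| 183 | Week 26 | Coincides with the scheduled visit | 1 |
| 184–232 | Week 26 | Loses to Day 183 | 49 |
| 233–323 | Week 40 | Not a model visit | 91 |
| 324–364 | Week 52 | Enters | 41 |

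- Enters: 13 + 48 + 41 = 102; 102/363 = 28%.
- Maps to no model visit: 70 + 91 = 161; 161/363 = 44%.
- Loses to a scheduled score: 49 + 49 = 98; 98/363 = 27%.

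Collecting the score is therefore necessary but not sufficient. Nobody leaving before Day 72 would be recovered by the schedule change alone.

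**The case against.** The best case for leaving the plan alone is that the gap is narrow. It concerns study withdrawal only, since those who stop treatment can continue to give scheduled scores. Leavers after Week 12 still contribute what they have. The precision at stake is small. SAP 7.1.3 makes no multiplicity adjustment and SAP 5 treats efficacy p-values as exploratory, so no confirmatory claim hangs on SGRQ. The SAP also uses early-withdrawal 6MWT and DLCO values only descriptively (7.2.4.2 and 7.2.4.3). All of this stands, and it limits the weight of the point. It does not answer why an uncollectable score for a key secondary endpoint should be forgone at a visit already taking place.

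A reader might also infer more than the documents support:

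- **That unequal withdrawal by arm by itself biases the SGRQ comparison.** It does not under missing at random (step 3). Bias needs leaving to depend on scores not seen, given those seen. That is plausible in a progressive disease but not shown.
- **That every leaver would supply a closing score.** Protocol 10.6 lists death and loss to follow-up among the reasons, and those participants cannot be relied on for one.
- **That an off-schedule SGRQ is thrown away.** SAP 5.2 considers all efficacy data for the summary tables. Such a score would be missing from the model, not from the report.
- **That widening the windows until they have no gaps would bring all withdrawal scores into the MMRM.** With midpoint cut-offs at Days 134 and 274 (midpoint of 183 and 365), scores on Days 86–134 (49 days) and 184–274 (91 days) would still lose to the on-time scheduled score: 140 of 363 days, 39%. Scores from Days 2–71 would be labelled Week 12, and one from Day 275 would be labelled Week 52, 90 days early.

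**Conclusion.** The omission is real and appears in both documents. A participant who withdraws from the study gives no closing SGRQ, SF-36 or UCSD-SOBQ score, and one with no Week 12, 26 or 52 score is absent from the SGRQ MMRM.

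The number affected cannot be derived from the documents. On an assumed 2–5% leaving before any post-baseline SGRQ, it is about 3–7 of 141, with an SE multiplier of about 1.01–1.03. Precision is therefore not the main issue. The issue is possible bias if leaving depends on worsening that earlier scores did not show; its size and direction cannot be stated from the documents, and the SAP has no SGRQ analysis that would reveal it. The point is moderate in weight and worth acting on because the remedy is cheap and the data cannot be obtained later.

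**What to change.** 1. Add SGRQ, SF-36 and UCSD-SOBQ to the Withdrawal column of Protocol Table 1 and SAP 11.2, and to note 9 in both.
2. Keep the planned MMRM and the SAP 5.2 windows as the main SGRQ analysis. Withdrawal scores on Days 72–84, 135–182 and 324–364 then enter it without further change if scheduled visits are on time.
3. Add to SAP 7.2.3.2 a sensitivity analysis that uses every SGRQ score, withdrawal scores included, at its actual time. One example is a random-coefficient model like the FVC model in SAP 7.2.2, with baseline SGRQ, treatment, time and treatment-by-time. This uses scores that map to Weeks 4, 8 or 40 or lose to the closest-day rule, without relabelling early scores as Week 12 or Week 52. It assumes a linear course, which is one reason to keep it as a sensitivity analysis.

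The cost is a few minutes of questionnaires at a visit already scheduled, plus one extra analysis. The change helps only for withdrawals that occur after it takes effect.
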